2.8.1.1 Adverse events of special interest / grouping of AEs

Allergic dermatitis, elevation in hepatic enzymes and neutropenia are the potential risks related to EMA401. Dizziness, headache, nausea, pre syncope and upper respiratory tract infections are the expected events related to EMA401. In addition suicidality and drug abuse related events will be adverse events of special interest. The search criterion for each of these risks and events will be defined based on MedDRA and on the Program Compound Case Retrieval The most recent Compound Case Retrieval Strategy (CRS) at the time of database lock will be used to determine the MedDRA search criteria to identify events of special interests.

2.8.2 Deaths

The primary reason for death will be summarized by system organ class and preferred term. All deaths will be listed.

2.8.3 Laboratory data

The summary of laboratory evaluations will be presented for three groups of laboratory tests: Hematology, Chemistry and Urinalysis.

The number and percentage of patients with newly occurring or worsening laboratory abnormalities meeting the clinically notable criteria at any post-baseline visit will be summarized by laboratory parameter. For a patient to meet the criterion of a newly occurring clinically notable value, the patient needs to have a baseline value that is not clinically notable for that parameter. For a patient to meet the criterion of a worsening clinically notable value, the patient needs to have a baseline value that is clinically notable and also have a worse post-baseline value. For patients with missing baseline value, any post-baseline notable value will be considered as newly occurring.

Incidence of newly occurring liver enzymes abnormalities and renal events will be summarized using the number and percentage of patients by treatment group. Notable laboratory values will be listed.

Laboratory assessments performed at the follow-up visits in the scope of the USM will not be included in the summaries but will be listed. That means, assessments reported 21 days after end of study date will not be included in the summary tables.

Liver function tests (LFT)

To evaluate potential drug-induced liver injury, the number and percentage of patients with newly occurring or worsening abnormalities in liver function tests at any time post-baseline will be summarized by treatment. The same approach as for notable laboratory values will be used to define newly occurring or worsening abnormalities in liver function tests.

When a criterion contains multiple laboratory parameters, the criterion will only be considered to have been met when all conditions occur at the same time (i.e., within the same sample). A case where all criteria are met at a post-baseline time point will be considered as newly occurring if the criteria are not met at baseline and will be considered as worsening if the criteria are met at baseline and at least one component is worsening from baseline irrespective of whether the other(s) are better.

Listings of patients with clinically notable LFT values will be provided.

The same analysis will be repeated for the Treatment withdrawal epoch.

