7.3 Liver safety monitoring

To ensure patient safety and enhance reliability in determining the hepatotoxic potential of an investigational drug, a standardized process for identification, monitoring and evaluation of liver events has to be followed.

The following two categories of abnormalities/adverse events have to be considered during the course of the study (irrespective of whether classified/reported as (S)AE):

- Liver laboratory triggers, which will require repeated assessments of the abnormal laboratory parameter
- Liver events, which will require close observation, follow-up monitoring and completion of the standard base liver CRF pages

Please refer to [Table 14-1 in Appendix 2](#) for complete definitions of liver laboratory triggers and liver events.

Every liver laboratory trigger or liver event as defined in [Table 14-1 of Appendix 2](#) should be followed up by the investigator or designated personal at the trial site as summarized below. Detailed information is outlined in [Table 14-2 in Appendix 2](#).

For the liver laboratory trigger:

- Repeating the liver function test (LFT) within the next week to confirm elevation

These LFT repeats must be performed using the central laboratory if possible. If this is not possible, then the repeats can be performed at a local laboratory to monitor the safety of the patient. Repeats laboratory must then be performed at central laboratory as soon as possible. If a liver event is subsequently reported, any local LFTs previously conducted that are associated with this event must be reported on the Liver CRF pages.

- If the elevation is confirmed, close observation of the patient will be initiated, including consideration of treatment interruption if deemed appropriate.

For the liver events:

- Repeating the LFT to confirm elevation as appropriate, [REDACTED]
- Discontinuation of the investigational drug if appropriate
- Hospitalization of the patient if appropriate
- A causality assessment of the liver event via exclusion of alternative causes (e.g., disease, co-medications)
- Specialist consultation at the discretion of the investigator.
- An investigation of the liver event which needs to be followed until resolution.

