LIVER EVENTS	
 • ALT or $\text{AST} > 5 \times \text{ULN}$ • $\text{ALP} > 2 \times \text{ULN}$ (in the absence of known bone pathology) • $\text{TBL} > 2 \times \text{ULN}$ (in the absence of known Gilbert syndrome) • ALT or $\text{AST} > 3 \times \text{ULN}$ and $\text{INR} > 1.5$ • Potential Hy's Law cases (defined as ALT or $\text{AST} > 3 \times \text{ULN}$ and $\text{TBL} > 2 \times \text{ULN}$ [mainly conjugated fraction] without notable increase in ALP to $> 2 \times \text{ULN}$) • Any clinical event of jaundice (or equivalent term) • ALT or $\text{AST} > 3 \times \text{ULN}$ accompanied by (general) malaise, fatigue, abdominal pain, nausea, or vomiting, or rash with eosinophilia • Any adverse event potentially indicative of a liver toxicity*

*These events cover the following: hepatic failure, fibrosis and cirrhosis, and other liver damage-related conditions; the non-infectious hepatitis; the benign, malignant and unspecified liver neoplasms
TBL= total bilirubin; ULN= upper limit of normal

Table 14-2 Follow Up Requirements for Liver Events and Laboratory Triggers

Criteria	Actions required	Follow-up monitoring
Potential Hy's Law case ^a	
 • Discontinue the study treatment immediately • Hospitalize, if clinically appropriate • Establish causality • Complete liver CRF 	
ALT, AST, TBL, Alb, PT/INR, ALP and γGT until resolution^c (frequency at investigator discretion)
 
ALT or AST		
$> 8 \times \text{ULN}$	
 • Discontinue the study treatment immediately • Hospitalize if clinically appropriate • Establish causality • Complete liver CRF 	
ALT, AST, TBL, Alb, PT/INR, ALP and γGT until resolution^c (frequency at investigator discretion)
 
$> 3 \times \text{ULN}$ and $\text{INR} > 1.5$	
 • Discontinue the study treatment immediately • Hospitalize, if clinically appropriate • Establish causality • Complete liver CRF 	
ALT, AST, TBL, Alb, PT/INR, ALP and γGT until resolution^c (frequency at investigator discretion)
 
> 5 to $\leq 8 \times \text{ULN}$	
 • Repeat LFT within 48 hours 	ALT, AST, TBL, Alb, PT/INR, ALP and

Criteria	Actions required	Follow-up monitoring

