Since the NPSI has not been studied in the EMA401-003 study, to mitigate the risk of uncertainty on the value of treatment difference and standard deviation, the effect size (treatment difference/ standard deviation) of NPSI total score has been considered for the calculation of power. The power of the study was calculated for different effect sizes ranging in 0.1, 0.5 for NPSI total score corresponding to 100 mg.

Under the assumptions of a 0.8 point treatment difference between 100 mg b.i.d. and placebo, a standard deviation as 2.6 for the primary efficacy variable and an effect size of 0.4 for 100

[figure not shown]
mg b.i.d. for the key secondary variable, N=200 patients per treatment arm will provide approximately 85% power to show that 100 mg b.i.d. is statistically significant over placebo for the primary efficacy variable, using the testing procedure mentioned in Figure 2-1. The power of showing the statistical significance of 100 mg b.i.d. dose in terms of the key secondary variable will be 84% under the same scenario. If we assume the treatment difference of 0.7 for the NRS as observed in the 4-week PoC study and the effect size for NPSI as 0.35, then the power for the primary objective will be 77% and that for the key secondary objective will be 72%. If the treatment difference between 100 mg b.i.d. and placebo is 0.9 for the NRS, and effect size is 0.45 for 100 mg b.i.d. for the NPSI, the power increases to 94% for the primary objective. The corresponding power for the key secondary objective increases to 93%.

4 Change to protocol specified analyses

An additional population, the mFAS population, has been defined.

The following analyses were specified in the protocol but will not be performed due the early termination of study:

- first and third supplementary analysis to the primary analysis
- tipping point analysis
- supplementary responder analyses
- ANCOVA analyses for BPI-SF, worst NRS pain score, ISI, [REDACTED]
- proportional odds model for PGIC
- analyses regarding maintenance effect of EMA401 over placebo
- time to "sustained" pain reduction
- Apart from analyses of clinical abnormalities summaries of laboratory data, vital signs and ECG intervals have been removed
- Shift tables of laboratory data
- No safety figures will be presented
- Bazett correction for QTc

The following analyses have been added:

- sensitivity analyses on modified full analysis population
- analyses of TEAEs with onset before study termination date

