5.3 Laboratory parameters derivations

Liver events defined by laboratory parameter abnormalities (additional non-lab criteria as provided in the protocol are ignored):

- ALT or AST $> 5 \times$ ULN
- ALP $> 2 \times$ ULN
- TBL $> 2 \times$ ULN
- ALT or AST $> 3 \times$ ULN and INR > 1.5
- ALT or AST $> 3 \times$ ULN and TBL $> 2 \times$ ULN AND ALP $\leq 2 \times$ ULN (Potential Hy's Law cases)
- ALT or AST $> 3 \times$ ULN

Renal events defined by laboratory parameter abnormalities (additional non-lab criteria as provided in the protocol are ignored):

- Serum creatinine increase 25 – 49% compared to baseline
- Serum creatinine increase $\geq 50\%$ compared to baseline
- New dipstick proteinuria $\geq 1+$
- New dipstick glycosuria $\geq 1+$ not due to diabetes
- New dipstick hematuria $\geq 1+$ not due to trauma
- Albumin- or Protein-creatinine ratio increase ≥ 2 -fold
- Albumin-creatinine ratio (ACR) ≥ 30 mg/g or ≥ 3 mg/mmol
- Protein-creatinine ratio (PCR) ≥ 150 mg/g or > 15 mg/mmol

Laboratory results will be reported in SI units.

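### The SAP's same-sample rule can leave a potential Hy's Law case out of the combined by-arm count when bilirubin (or INR) crosses its limit after ALT/AST has returned to 3 × ULN or below

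*SAP*

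**What the plan says.** SAP 2.8.3, under liver function tests, gives the purpose of the summary: "To evaluate potential drug-induced liver injury, the number and percentage of patients with newly occurring or worsening abnormalities in liver function tests" at any time after baseline. For a criterion made of several laboratory parameters it adds that "the criterion will only be considered to have been met when all conditions occur at the same time (i.e., within the same sample". It also promises: "Listings of patients with clinically notable LFT values will be provided".

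SAP 5.3 lists the criteria. Two combine several parameters in a way that the rule restricts: "Potential Hy's Law cases" (ALT or AST above 3 × ULN, TBL above 2 × ULN, ALP at or below 2 × ULN), and ALT or AST above 3 × ULN with INR above 1.5. Separate criteria cover ALT/AST above 3 × ULN, ALT/AST above 5 × ULN, TBL above 2 × ULN and ALP above 2 × ULN.

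Protocol Appendix 2 (Table 14-1, and footnote a of Table 14-2) defines a potential Hy's Law case with the same thresholds and says nothing about when the components must occur. SAP 5.3 announces that non-laboratory protocol criteria are ignored; a timing condition on laboratory values is not one of those. SAP section 4, which records departures from the protocol's analyses, does not mention the same-sample rule. It does record that "No safety figures will be presented".

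On repeat liver tests, Protocol 7.3 prefers the central laboratory, but where that is not possible "the repeats can be performed at a local laboratory to monitor the safety of the patient". Local results tied to a liver event must go on the liver CRF pages.

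**The concern.** The LFT table is the planned by-arm summary for judging drug-induced liver injury, and both documents name hepatic enzyme elevation as a potential risk of EMA401 (Protocol 9.5.2.2, SAP 2.8.1.1). A potential Hy's Law case is the most serious pattern that the table is meant to show. The rule counts it only if ALT/AST and TBL are both over their limits in one blood draw.

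A patient whose ALT/AST elevation and later TBL elevation fall in different samples meets the protocol's thresholds, but enters the SAP table as separate single-marker findings. The INR criterion is in a weaker position still: SAP 5.3 has no row for INR alone, so the INR half of such a pair has no single-marker row to fall back on.

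The reduced reporting after early termination leaves little else that would show the pairing. SAP section 4 removes laboratory shift tables, laboratory summaries other than abnormalities, and all safety figures. A reader would have to link the elevations patient by patient from the listing.

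**Working it through.** The documents give no figure that depends on this rule, so there is no planned result to reproduce. The check applies the rule to example courses and then shows what one case means at the actual trial size.

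**Step 1. Inputs.** Thresholds from SAP 5.3; timing rule from SAP 2.8.3; comparison definition, without timing, from Protocol Tables 14-1 and 14-2. The courses are invented for illustration, in multiples of ULN. They are placed at Weeks 6 and 8 because Table 6-1 schedules chemistry at both visits.

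| Course | Week 6 (ALT / TBL / ALP) | Week 8 (ALT / TBL / ALP) | Same-sample rule | Linked across samples |
|---|---|---|---|---|
| A | 6 / 1.2 / 1.2 | 2.5 / 2.6 / 1.3 | not counted | counted |
| B | 6 / 1.2 / 1.2 | 3.4 / 2.6 / 1.3 | counted (Week 8) | counted |
| C | 6 / 2.4 / 1.2 | not needed | counted (Week 6) | counted |

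Course A fails the same-sample rule twice: at Week 6 TBL is 1.2, not above 2, and at Week 8 ALT is 2.5, not above 3. The patient still appears in the rows for ALT/AST above 3, ALT/AST above 5 and TBL above 2 × ULN. Course B marks the boundary: a falling ALT that is still above 3 × ULN when TBL crosses is counted. The gap therefore exists only when ALT/AST is at or below 3 × ULN in every sample that shows TBL above 2 × ULN.

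**Step 2. INR.** The logic is the same. ALT of 6 × ULN in one sample, then ALT of 2.5 × ULN with INR above 1.5 in the next, is not counted in the combined INR row.

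**Step 3. One case at this trial's size.** SAP Amendment 1 gives 137 randomized. Arm sizes are not stated; 1:1 allocation suggests 137 / 2 = 68.5, so 68 or 69 per arm is assumed. Exact (Clopper-Pearson) 95% intervals:

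- 0 cases: upper limit = 1 − 0.025^(1/n), which is 5.28% for n = 68 and 5.21% for n = 69.
- 1 case: 1/68 = 1.47% (0.04% to 7.92%); 1/69 = 1.45% (0.04% to 7.81%).

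**Step 4. Two neighbouring rules in the SAP.** SAP 2.8 reports the treatment and withdrawal epochs separately, and 2.8.3 repeats the LFT analysis for the withdrawal epoch. An ALT rise at Week 12 and a TBL rise at Week 13 would be split unless a linking rule spans both. SAP 2.8.3 also keeps laboratory values from the urgent-safety-measure follow-up, reported 21 days after the end of study date, out of the summaries. A late TBL value there is uncounted under either rule, though it is listed.

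**The case against.** The best defence is that the plan contains no contradiction. The protocol is silent on timing, its wording can be read as concurrent, and Protocol 9.5.2 leaves details of the laboratory analysis to the SAP. The SAP then settles the matter with an explicit, prespecified rule. This stands: the rule is a narrow choice, not an error, and its absence from section 4 is a matter of transparency.

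It is also true that the patient does not vanish. The single-marker rows and the LFT listing remain, TBL above 2 × ULN is a liver event in its own right in Table 14-1, and the DMC reviews narratives for clinically significant hepatic abnormalities. With 137 patients, a diligent reader can link the values. None of this produces a combined count by arm, which is what the table is for.

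Some stronger readings are tempting but lack support:

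- **That the visit spacing gives a probability of missing a case.** It does not. A sampled ALT/AST elevation triggers repeat tests under Table 14-2 (within 48 hours for more than 5 to 8 × ULN, within a week for asymptomatic values of more than 3 to 5 × ULN), so routine intervals are the wrong model.
- **That study drug is stopped, so ALT/AST falls before bilirubin rises.** Table 14-2 does not stop drug at every elevation, and neither document describes the usual order of these markers. The counting gap needs only that such a course can occur.
- **That the urgent safety measures were hepatic.** The SAP does not give the reason.
- **That local LFTs are excluded from the summary.** The SAP does not say whether they enter.

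**Conclusion.** The point holds as a reporting gap. The same-sample rule adds a restriction that the protocol's definition does not contain, and it can make the by-arm count of potential Hy's Law cases, and of the ALT/AST-with-INR criterion, too low. The error runs in one direction only: the rule can remove cases from the combined row but cannot add any.

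The number affected cannot be estimated from the documents and may be zero. If there is one such patient, an arm of 68 or 69 moves from 0% to about 1.5%. A reader might infer that one missed case would overturn the liver safety conclusion. The documents do not support that; it could alter how the finding is described, but the intervals for zero and one case overlap widely. The figures assume near-equal arms, with everyone randomized in the safety population.

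The change is worth making because the risk is a named one and the remedy is cheap.

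**What to change.** In SAP 2.8.3 and 5.3, keep the same-sample row and add a second, linked row:

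1. Count a patient with ALT or AST above 3 × ULN in one post-baseline sample and TBL above 2 × ULN in the same or another post-baseline sample. If a time window is preferred, fix its length before unblinding and declare it as an assumption, since the documents give none.
2. Require ALP at or below 2 × ULN in at least one sample that shows the ALT/AST elevation. Worded this way, every same-sample case is also a linked case when no window limits it or when the window includes the same day.
3. Do the same for ALT/AST above 3 × ULN with INR above 1.5, without the ALP condition.
4. Let the link cross the treatment and withdrawal epochs, and state which epoch and treatment group receive the count, for example those of the ALT/AST elevation.
5. State that local LFTs recorded on the liver CRF pages are included.
6. Flag in the listing any pair completed only by an urgent-safety-measure follow-up value that the summaries leave out.
7. Record both counting rules in SAP section 4.

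The cost is some wording and one more table row for each of the two criteria. The downside is that an unrelated later bilirubin rise may occasionally be flagged; the planned listing lets the reader resolve it, and the unchanged same-sample row shows the stricter count beside it.

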3.2 Rationale for study design

This study will evaluate the safety and efficacy of EMA401 100 mg b.i.d. in the treatment of PDN.

The aim is to estimate the treatment effect of the investigational drug (EMA401 100 mg b.i.d.) compared to placebo, for the target population on the primary pain parameter. The treatment effect of interest accounts for post-randomization events in a way that reflects their possible relationship to the investigational treatment. In particular, the treatment effect of interest:

- shall not be confounded by events which are deemed non informative on the effect of the study medication, even if they may have the potential to confound it (e.g. some changes in concomitant medications), and
- shall account for events reflecting the unfavorable outcome when patients are unable to continue taking the study medication or unable to benefit from it (such as study treatment discontinuations for specific reasons).

Further details are provided in [Section 9.4.2](#).

The standard methodology for the purpose of evaluating safety and efficacy based on the above treatment effect is to conduct a double-blind, placebo-controlled, randomized, parallel group study. Twelve weeks of exposure is required for assessment of treatment response and registration in chronic pain conditions, as indicated in Food and Drug Administration (FDA) and European Medicines Agency (EMA) guidelines. The quarterly unblinded DMC review of safety data, together with clinical assessments every two weeks will ensure patient safety, according to the DMC Charter.

The study will evaluate the potential for a rebound effect of EMA401 in efficacy and withdrawal effect in safety after study drug discontinuation during a treatment withdrawal period designed to minimize bias via a randomized withdrawal design.

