2.1.1 General definitions

Investigational drug and study treatment

The investigational drug, EMA401, will be provided as capsules. The following oral dosage strengths will be used: 50 mg.

EMA401 and placebo will be identical in appearance .

For all treatment groups, each dose will be self-administered orally as two capsules with a full glass of non-carbonated water twice daily, consisting of a morning dose and an evening dose.

The following abbreviated treatment groups, independently of cohort number, will be used as the headers in the tables for the double-blind Treatment epoch:

- Placebo b.i.d.
- EMA401 100 mg b.i.d.

The following abbreviated treatment groups will be used as the headers in the tables for the double-blind Treatment withdrawal epoch:

- Placebo b.i.d. -> Placebo b.i.d.
- EMA401 100 mg b.i.d. -> EMA401 100 mg b.i.d.
- EMA401 100 mg b.i.d. -> Placebo b.i.d.

Date of first and last administration of study drug

The date/time of first administration of study drug is defined as the first date/time of administration as per Dosage Administration Record eCRF. The date/time of last administration of study drug is defined as the last date/time when a dose is administered as per Dosage Administration Record eCRF. This value has to be compared to the "End of study treatment" as recorded on the corresponding eCRF. In case of different dates, the latest will be used as treatment end.

For subjects with missing first dose date, the randomization date will be considered as reference start date.

Study day

The study day, describes the day of the event or assessment date, relative to the reference start date which is the date of first administration of study drug.

The study day is defined as:

- The date of the event (visit date, onset date of an event, assessment date etc.) – reference start date + 1 if event is on or after the reference start date.
- The date of the event (visit date, onset date of an event, assessment date etc.) – reference start date if event precedes the reference start date.

Baseline

For safety and efficacy evaluations, the last available assessment (either scheduled or unscheduled) before the first administration of study drug and after the screening visit is defined as “baseline” assessment. If patients have no value prior to first administration of study drug the baseline result will be missing.

Post-baseline

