For safety and efficacy evaluations all assessments after the first administration of study drug are defined as “post-baseline” assessment.

Change and percent change from baseline for continuous parameter.

Change from baseline and percent change from baseline will only be summarized for subjects with both baseline and post-baseline values and will be calculated as:

change from baseline = post-baseline value – baseline value

percent change from baseline = $100 * \text{change from baseline} / \text{baseline value}$.

For summary statistics the raw values (and not imputed values) will be used.

Study periods and date of last contact

The overall observation period will be divided into three mutually exclusive segments:

- A screening phase of up to 4 weeks
- A double-blind treatment phase starting with first dose of study drug at Visit 101 and covering 12 weeks of treatment.
- A double-blind treatment withdrawal phase for one week starting after 12 weeks of treatment with Visit 201.

Inferential analysis will be performed on either only treatment phase or on both treatment and treatment withdrawal phase separately. It is never the case that both phases will be pooled together.

Visit windows

Visit windows will be applied for all measurements except NRS scores. The definition of seamless windows can be found in the following [REDACTED] location [REDACTED]

[figure not shown]
[REDACTED] The most recent version of this document available before the database lock will be used to determine the visit windows for baseline and post baseline visits and treatment discontinuation visit mapping.

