2.8 Safety analyses

Safety analyses will be conducted using the safety (SAF) population. Patients will be analysed by the actual treatment they received. All the safety analyses including AEs, vital signs, laboratory parameters, ECGs [REDACTED] will be reported for double-blind treatment period as well as for the treatment withdrawal period separately.

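### In the withdrawal-epoch laboratory, liver and QTc tables, abnormalities carried over from treatment count as newly occurring, because the only reference value is the pre-treatment baseline

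*SAP*

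**What the plan says.** SAP 2.1.1 gives a single baseline for safety and efficacy: "the last available assessment (either scheduled or unscheduled) before the first administration of study drug and after the screening visit is defined as" baseline. First administration is the first dose of the whole study: "The date/time of first administration of study drug is defined as the first date/time of administration as per Dosage Administration Record eCRF". Everything later is post-baseline: "For safety and efficacy evaluations all assessments after the first administration of study drug are defined as" post-baseline.

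Under SAP 2.8.3, a value is newly occurring when it is notable after baseline and "the patient needs to have a baseline value that is not clinically notable for that parameter". The liver criteria that combine several parameters use the same test. At the end of the liver subsection: "The same analysis will be repeated for the Treatment withdrawal epoch". SAP 2.8 adds that safety analyses, including laboratory values and ECGs, "will be reported for double-blind treatment period as well as for the treatment withdrawal period separately". SAP 2.8.4.1 carries the laboratory approach over to notable QTc values.

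Protocol 3.2 gives the withdrawal week the purpose of evaluating, on the safety side, a "withdrawal effect in safety after study drug discontinuation during a treatment withdrawal period designed to minimize bias via a randomized withdrawal design". Patients on EMA401 are randomized 1:1 to continue or to switch to placebo, and placebo patients stay on placebo.

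**The concern.** Neither document defines a Week 12 reference or sets aside abnormalities already present when a patient enters the withdrawal epoch. The SAP does not expressly say that the pre-treatment baseline is kept for that epoch, but it has no other baseline and it repeats the same analysis.

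A hypothetical record shows the result. ALT is normal on Day 1, 4 x ULN at Weeks 8 and 12 on EMA401, and 3.5 x ULN at Week 13 after the switch to placebo. The rule counts this as newly occurring in the treatment epoch and again in the withdrawal epoch, although nothing began in that week and the value was falling. Such a record can arise: ALT or AST above 3 x ULN is a tabulated criterion (SAP 5.3), and the actions in Protocol Table 14-2 for an asymptomatic value above 3 and up to 5 x ULN do not include stopping study drug.

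Adverse events, by contrast, are allocated to an epoch by start date (SAP 2.8.1), so the adverse event and laboratory tables could disagree about one patient. Hepatic enzyme elevation is a named potential risk. SAP section 4 also removes the shift tables and the laboratory and ECG summaries other than those of clinical abnormalities, so little else in the tables would show that a value was carried over.

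**Working it through.** **Step 1: all patterns.** The documents give no figure that depends on this rule, so there is none to reproduce. The eight combinations of status at baseline, Week 12 and Week 13 (N = not notable, A = notable) are:

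| Baseline | Week 12 | Week 13 | New in withdrawal epoch, SAP rule | New, Week 12 reference |
|---|---|---|---|---|
| N | N | N | no | no |
| N | N | A | yes | yes |
| N | A | N | no | no |
| N | A | A | **yes** | **no** |
| A | N | N | no | no |
| A | N | A | **no** | **yes** |
| A | A | N | no | no |
| A | A | A | no | no |

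The two rules differ on two patterns. N-A-A is carry-over labelled as an onset. A-N-A is a recurrence that the SAP rule can count only as worsening, and only if it is worse than baseline.

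**Step 2: size under assumptions.** The following inputs are assumed and do not come from the documents: prevalence π of a notable value (2% to 10%), within-patient correlation ρ (0.5 to 0.9), and a drug shift δ of 0 or 0.5 SD that persists in full at Week 13. The model is a normal random intercept b with threshold z = Φ⁻¹(1 − π). Given b, the chance of a notable value is p = 1 − Φ((z − √ρ·b)/√(1 − ρ)) at baseline. After baseline it is q, the same expression with z − δ in place of z. Averaging over b:

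- new rate at Week 13, SAP rule: E[(1 − p)q]
- share of these already notable at Week 12: E[(1 − p)q²] / E[(1 − p)q]
- new rate at Week 13, Week 12 reference: E[(1 − q)q]

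Numerical integration gives:

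| π, ρ | SAP new rate, δ = 0 | Share carried over, δ = 0 | SAP new rate, δ = 0.5 | Share carried over, δ = 0.5 | Rise in SAP rate | Rise with Week 12 reference |
|---|---|---|---|---|---|---|
| 2%, 0.5 | 1.66% | 14% | 5.32% | 23% | 3.2-fold | 2.7-fold |
| 2%, 0.9 | 0.84% | 34% | 4.24% | 54% | 5.0-fold | 2.5-fold |
| 10%, 0.5 | 6.76% | 25% | 16.31% | 39% | 2.4-fold | 1.8-fold |
| 10%, 0.9 | 3.11% | 40% | 12.42% | 61% | 4.0-fold | 1.7-fold |

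With δ = 0, q equals p, so both rules give the same total rate: N-A-A and A-N-A are equally likely and offset each other. The SAP rule then picks the wrong patients but does not inflate the count.

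**Step 3: scale of this trial.** With 137 randomized, each EMA401 withdrawal arm can hold at most about 137/4 ≈ 34 patients. One carried-over case is 1/34 ≈ 3 percentage points.

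**The case against.** The strongest reply is that these tables are not the plan's stated withdrawal-effect analysis. SAP 2.8.1 assigns that to drug abuse-related adverse events, and 2.8.3 gives drug-induced liver injury as the purpose of the liver table. Comparison with the pre-drug value is reasonable for liver injury. That stands, and it is a reason to keep the pre-treatment baseline alongside a Week 12 split. It does not make a persisting value an onset of the withdrawal week.

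Four stronger readings are tempting, and the documents do not support them:

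- *The withdrawal-epoch new rate rises 2.4- to 5-fold because of carry-over alone.* With a Week 12 reference the rate still rises about 1.7- to 2.7-fold, because the assumed shift continues to produce fresh abnormalities at Week 13.
- *The withdrawal tables show mostly carry-over.* With no drug effect, 60% to 86% of the new cases were not notable at Week 12.
- *The comparison of stopping with continuing is biased by carry-over.* The two arms are randomized, so abnormalities present at Week 12 are balanced in expectation. They dilute the contrast. The comparison that carry-over raises is with placebo-placebo, which does not isolate stopping.
- *The vital-sign table has the same defect.* SAP 2.8.4.2 tabulates clinically notable values and uses the newly occurring label only for an additional listing.

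Some limits on impact also stand. Several liver events require study drug to be stopped, so carry-over should fall mostly in milder categories. The column header shows prior EMA401 exposure. Notable laboratory and ECG values are listed, so a careful reader could find the persisting cases. No test or decision rule depends on these tables.

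**Conclusion.** The concern holds as a labelling defect in the withdrawal-epoch laboratory, liver and QTc tables. It follows from the SAP's definitions without any numerical assumption: carry-over is called new, and recurrence after a normal Week 12 value is not. The share of mislabelled cases cannot be derived from the documents. The ranges of about 14% to 40% with no drug effect and 23% to 61% with a persisting 0.5 SD shift rest entirely on the assumed prevalence, correlation and shift. The practical stake is descriptive: in arms of at most about 34 patients, one or two misread cases would visibly change a percentage. The change is worth making because it is cheap and the tables would otherwise misdescribe what happened after stopping.

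**What to change.** Add to SAP 2.8.3 and 2.8.4.1 that, in the withdrawal-epoch laboratory, liver and absolute-threshold QTcF (above 500 msec) tables, each notable Week 13 value is classified by status at the last assessment on or before the first withdrawal-epoch dose. Show two rows: new since Week 12, and persisting from the treatment epoch.

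Keep the pre-treatment baseline for all treatment-epoch tables and for criteria that are themselves changes from baseline, such as the QTcF increase above 60 msec and the percentage rises in creatinine. For vital signs, apply the split only to the newly occurring listing.

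The cost is one SAP sentence and one dataset flag. No new data are needed: Protocol Table 6-1 schedules chemistry, hematology and ECG at Weeks 12 and 13, and its footnotes place the Week 12 ECG and samples before that morning's dose, with withdrawal medication starting that evening.
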